2.6.2 Safety analyses

The safety analyses described in this section will be performed for the SAF.

2.6.2.1 Adverse events (AEs)

Treatment emergent adverse events (TEAEs) during the double-blind period are defined as any AE with start date on or after the start date of the first dose of the study drug during the double-blind period.

The number and percentage of patients with the following types of treatment emergent adverse events during the double-blind period will be provided by primary SOC, PT and treatment group

in separate tables: AEs, SAEs, AEs leading to study drug discontinuation, AEs suspected to be study drug related, and AEs leading to study drug interruption. TEAEs during the double-blind period will also be summarized by primary SOC, PT, maximum severity and treatment group. The most common TEAEs ($\geq 10\%$ in any treatment group) during the double-blind period will be presented by PT in descending order of frequency in the investigational study drug arm, LIK066 50 mg qd.

The following rules apply to the above AE summaries:

- If a patient has multiple AEs within a primary system organ class during the double-blind period, the patient will be counted only once in that primary system organ class
- If a patient has multiple occurrences of an AE with the same PT during the double-blind period, this patient will be counted only once at that PT level.
- An AE with increased severity should be considered and recorded as a new AE.

All TEAEs during the double-blind period will be summarized descriptively by primary SOC, PT and treatment in the following subgroups: baseline LVEF $< 45\%$ vs. $\geq 45\%$.

All AEs will be listed at the individual patient level. The listings will include those AEs reported during the screening and run-in period, and AEs reported after study discontinuation for those who discontinue the study prior to the end of the study.

Deaths occurred during the double-blind period will be summarized descriptively (using number and percentage of patients) by primary SOC and principal cause of death. All deaths will be listed.

2.6.2.2 Adverse events of special interest / grouping of AEs

AEs of special interest that are defined in the Development Safety Profiling Plan (DSPP) can be found in the electronic case retrieval sheet (eCRS) stored in GPS.

The pre-defined issues of special interest for LIK066 including identified risks, potential risks and special assessments are listed below:

- Bone fractures
- Cardiotoxicity
- Diarrhea
- Electrolyte disturbances
- Genital infections
- Hepatotoxicity
- Hypersensitivity
- Hypoglycemia
- Impaired renal function
- Increased LDL
- Intravascular volume depletion

- Ketoacidosis
- Lower limb amputation
- Pre-amputation events
- Malignancy
- Pancreatitis
- Urinary tract infections
- Venothrombotic and embolic events

Treatment-emergent AEs of special interest will be summarized for double-blind period, by risk category, preferred term and treatment group. Treatment emergent AEs of special interest during the double-blind period will also be summarized descriptively by risk category, preferred term and treatment group in the following subgroups: baseline LVEF < 45% vs. \geq 45%.

Additional analyses for the pre-defined risks of diarrhea, ketoacidosis and hypoglycemia will be performed as described below:

Diarrhea events

Number of days with diarrhea events will be calculated for all patients with at least one diarrhea incidence and will be summarized descriptively by treatment.

- Number of days for one diarrhea incidence = AE end date – AE start date +1.
- Number of days with diarrhea events for a patient = sum of days on diarrhea over all incidences that occurred in the double-blind period.

The number and percentage of patients with diarrhea events during the double-blind treatment period will also be summarized by treatment over time in the following time window: 0 - < 2, 2 - < 4, 4 - < 8, 8 - < 12, 12 - < 16, 16 - < 24, \geq 24 weeks.

Ketoacidosis events of special interest

All cases of ketoacidosis will be adjudicated by an independent committee. The frequencies and percentages of the adjudication confirmed ketoacidosis events will be provided by treatment.

The site-reported ketoacidosis events will also be summarized by treatment. In addition, the ketoacidosis events will be listed at individual patient level, with the site-reported event profile and symptoms and the adjudication outcome displayed as well.

Hypoglycemic events of special interest

Hypoglycemic events entered into the study Hypoglycemic event eCRF are included in all of the AE summaries in [Section 2.6.2.1](#).

In addition, there are two categories of clinically significant hypoglycemic events defined:

- **Severe hypoglycaemia:** An event, requiring assistance of another person (third party assistance) to actively administer carbohydrate, glucagon, or other corrective actions, confirmed or not by a blood glucose measurement

- **Other clinically significant hypoglycaemia:** Plasma glucose < 3.0 mmol/l (54 mg/dl) with or without typical symptoms of hypoglycaemia, and which is handled by the subject himself/herself.

Hypoglycemia classification is included in the Appendix [Table 5-1](#).

Patients reporting at least one clinically significant hypoglycemic event, and the subgroup of patients reporting ≥ 2 such events, patients discontinued study medication or withdrew from the study due to clinically significant hypoglycemic events, patients reporting severe hypoglycemic events, and patients reporting other clinically significant hypoglycemic events will be summarized by numbers and percentages in each treatment group. The exposure-adjusted incidence rates, relative risks and the related 95% confidence intervals of LIK groups versus placebo for the overall, severe and other clinically significant hypoglycemic incidences will be calculated respectively, and presented along with other safety risks/events of interest.

The clinically significant hypoglycemic events will also be summarized by event profile as follows:

- Severity (Mild, Moderate, Severe)
- Meeting the definition of an SAE (Yes, No)
- Seriousness (Death, Life threatening, Requires or prolongs hospitalization, Congenital anomaly or birth defect, Significant disability, Other medically important serious event)
- Discontinuation due to hypoglycemic events (Yes, No)
- Relationship to the study treatment (No, Investigational treatment, Other study treatment, Both and/or indistinguishable)
- Action taken with study treatment (Dose increased, Dose not changed, Dose reduced, Drug interrupted, Drug withdrawn, Unknown, Not applicable)
- Medication or therapy taken (Yes, No)
- Outcome (Not recovered/not resolved, Recovered/resolved, Recovered/Resolved with sequelae, Fatal, Unknown)
- Time of the day in 24-hour clock (>00:00–06:00, >06:00–12:00, >12:00–18:00, or >18:00–24:00)
- Time between last meal and event
- Time between last dose and event
- Precipitating factors (None, Missed/delayed meal, Strenuous exercise, Alcohol consumption, Other)
- Third party assistance (Yes, No)
- Medical assistance received (Yes, No)

A listing of AEs of special interest will be presented by treatment group and patient number.

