### **3.6 Risks and benefits**

The risk to patients in this study will be minimized by compliance with the eligibility criteria and study procedures, and close clinical monitoring.

Further information is provided in the Investigator Brochure (IB).

Publications on SGLT2 inhibition in subjects with T2DM treated with selective SGLT2 inhibitors reported higher incidences of urinary tract infections (UTIs) and genital mycotic infections compared with placebo (Bailey et al, 2010; Nauck et al, 2011; Nyirjesy et al, 2012) and some genital infections have been seen in healthy volunteers and patients treated with LIK066. SGLT2 inhibition may result in hypotension in elderly subjects, in subjects with low blood systolic pressure, or if on diuretics, ACE inhibitors, or ARBs. Patients with T2DM treated with antidiabetic agents, especially with sulphonylurea or insulin, may be at an increased risk of hypoglycemia. In rare cases treatment with SGLT2 inhibitors may be complicated by ketoacidosis (Rosenstock et al, 2015). However, this has not been seen to date in clinical studies with LIK066. In long-term clinical studies in patients with T2DM with CVD or at high risk for CVD, an increase in cases of lower limb amputation (primarily of the toe) has been observed with the SGLT-2 inhibitor canagliflozin (Neal et al, 2017). No lower limb amputations have been seen in LIK066 studies to date, but since this risk may constitute a possible class effect, patients with a higher risk for amputation events should be instructed on routine preventative foot care and maintaining adequate hydration. The only preclinical/class safety issues which have been seen in clinical studies with LIK066 are the GI side effects and vulvovaginal infections. A detailed description of safety in humans with LIK066 is found in the LIK066 IB.

Hematology and biochemistry tests will be monitored at each study visit after randomization and study drug can be discontinued for clinically significant laboratory change or abnormality as per investigator's judgment. Detailed criteria for follow-up in case of a liver event are defined in [Appendix 2](#). To prevent UTIs and genital infections, patients will be instructed to pay attention to genital hygiene and have appropriate hydration. If UTI and/or genital infections occur, treatment will be initiated as appropriate at the investigator's discretion.

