### 4.1 Inclusion criteria

Patients eligible for inclusion in this study must fulfill all of the following criteria:

1. Written informed consent must be obtained before any assessment is performed.
2. Male or female outpatients,  $\geq 18$  years of age at Visit 1.
3.  $\text{BMI} \geq 22 \text{ kg/m}^2$  at Visit 1.
4. Type 2 diabetes with  $\text{HbA1c}$  between 6.5% and 10.0% at Visit 1.
5. Documented symptomatic chronic heart failure (NYHA II-IV) with at least one of the following symptoms at the time of Visit 1:
  - Dyspnea on exertion
  - Orthopnea
  - Paroxysmal nocturnal dyspnea
  - Peripheral edema
6. Plasma NT-proBNP  $> 300 \text{ pg/ml}$  at Visit 1.
7. Patients receiving ACEi, ARBs, MRAs, ARNi and/or  $\beta$ -blockers must be on a stable dose of these medications during the 1 month period prior to Visit 1.
8. Patients must be on diuretic therapy prior to Visit 1 (flexible dosing is permitted).
9. Controlled systolic BP defined as a target systolic BP less than 140mmHg; systolic BP up to and including 160mmHg if patient is on three or more medications to control BP, at randomization (Visit 201).
10.  $\text{eGFR} \geq 45 \text{ ml/min/1.73m}^2$  at Visit 1 (calculated by the Modification of Diet in Renal Disease formula (MDRD)).
11. Serum potassium  $\leq 5.3 \text{ mM}$  at Visit 1.

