### **9.5.2 Safety variables**

The safety assessments are listed below:

- Identified and potential risks
- AEs and SAEs
- Vital signs
- Laboratory evaluations
- ECG
- 24h urinary calcium and phosphate excretion (in a subset of patients)
- BMD (in a subset of patients)

The incidence of treatment emergent AEs (events started on or after the study treatment start date during Epoch 3 will be summarized by primary system organ class and preferred term. Summaries will also be provided by severity and relationship to study medication. The incidence of death, SAEs, and AEs leading to discontinuation will be summarized separately by primary system organ class and preferred term. The number and percentage of patients with AEs related to identified and potential risks will be summarized by treatment.

Laboratory data will be summarized by presenting shift tables, summary statistics of raw data and change from baseline and by flagging of notable values in data listings.

[figure not shown]
Other safety assessments (e.g., vital signs and ECG) will be summarized descriptively by treatment as appropriate. Data will be listed, notable values will be flagged, and other information collected will be listed as appropriate.

[figure not shown]
Summary statistics (n, mean, standard deviation, median, Q1, Q3, minimum, and maximum) will be provided by visit and treatment for the 24h urinary calcium, phosphate excretion and BMD from the sub-study, for measurement at each visit and change from baseline values.

The above analyses will be performed for the SAF for data collected during Epoch 3 for *Week 12 analysis*. For *End of study analysis*, these analyses will be carried out for data collected during Epoch 3 + Epoch 4.

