2.2 Analysis sets

The following analysis populations will be defined for statistical analysis. Subjects without valid written informed consent will be excluded from all analysis sets. Rules of exclusion criteria of analysis sets are detailed in [Appendix 5-4](#). The analysis sets are defined as follows:

Screened set (SCR) – All patients who signed the informed consent. The SCR includes only unique screened patients, i.e., in the case of re-screened subjects only the chronologically last screening data is counted.

Enrolled set (ENR) – All patients who entered the run-in epoch.

Randomized set (RAN) – All patients who received a randomization number, regardless of receiving trial medication.

Safety set (SAF) (double-blind phase) – All patients who received at least one dose of double-blind study drug. Patients will be analyzed according to treatment received. Treatment received will be considered identical to the randomized treatment if the patient has received at least one dose of the randomized treatment.

Full analysis set (FAS) – All patients in RAN who were not mis-randomized*. Following the intent-to-treat (ITT) principle, patients are analyzed according to the treatment they have been assigned to at the randomization.

* Mis-randomized patients are those who have not been qualified for randomization and who have been inadvertently randomized into the study, but have not received double-blind study drug. Mis-randomized patients are defined as cases where IRT contacts were made by the site either prematurely or inappropriately prior to confirmation of the patient’s final randomization eligibility and double-blind medication was not administered to the patient. These patients were subsequently discontinued from the study.

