LIK high dose (n=124) versus placebo (n=124)*	0.5%	1	96%
Any LIK low dose (n=62) versus placebo (n=124)*	0.5%	1	85%

*assuming 10% information loss due to drop-out.

Table 3-3 Comparison of LIK versus empagliflozin

	Expected treatment difference	SD	Probability of the 95% confidence interval upper bound < 0.4%
LIK high dose (n=124) versus EMPA (n=124)	0	1	84%
Any LIK low dose (n=62) versus EMPA (n=124)	0	1	68%

*assuming 10% information loss due to drop-out.

The calculations in Table 3-2 and 3-3 were performed using nQuery 7.0. No multiple testing adjustment was applied.

4 Change to protocol specified analyses

Due to the early termination of the CLIK066B2204 study, the following major changes to the protocol specified analyses have been made in the SAP amendment 1:

- “Week 12 Analysis” and “End of Study Analysis” as defined in the study protocol are no longer applicable. The analyses for the abbreviated CSR will be carried out after the completion of the study.
- MCP-Mod will not be performed for the primary endpoint change in log-transformed NT-proBNP at Week 12. Instead, MMRM will be performed as an exploratory analyses for NT-proBNP. See details in Section 2.5.
- Summary statistics will be provided for selected efficacy endpoints. All efficacy endpoints will be listed. See details in Sections 2.5, 2.6.1.2, 2.7.1.2.
- Subgroup analyses will only be performed for demographics and baseline characteristics, primary and key secondary efficacy endpoints summary statistics, AEs and AEs of special interest, in the subgroups LVEF <45% vs. >= 45%.

5 Appendix

The missing or partially missing AE start/end date and concomitant medication start/end date will be imputed using the Novartis ADaM Governance Board (AGB) global standard approach. Details will be provided in the study Programming Datasets Specifications.

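### Vulvovaginal infection terms are tabulated on an all-patient denominator; adding a sex-specific denominator is a cheap way to report the rate in women

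*SAP*

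**What the plan says.** Protocol 3.6 (Risks and benefits) states: "The only preclinical/class safety issues which have been seen in clinical studies with LIK066 are the GI side effects and vulvovaginal infections". The trial enrols both sexes ("Male or female outpatients", Protocol 4.1), with no target or expected share of women. Randomisation is stratified by region and LVEF, not by sex (Protocol 5.3).

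On the analysis set, SAP 2.6.2 says "The safety analyses described in this section will be performed for the SAF", and SAP 2.2 defines the SAF as "All patients who received at least one dose of double-blind study drug", with no restriction by sex.

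On the measure, Protocol 9.5.2 says "The number and percentage of patients with AEs related to identified and potential risks will be summarized by treatment". SAP 2.6.2.1 gives numbers and percentages of patients with AEs by system organ class, preferred term and arm. It adds a table of the most common events, restricted to terms reaching 10% ("in any treatment group) during the double-blind period will be presented by PT in descending order of frequency"). SAP 2.6.2.2 lists genital infections among the risks of special interest and says "Treatment-emergent AEs of special interest will be summarized for double-blind period, by risk category, preferred term and treatment group". Further analyses there cover diarrhea, ketoacidosis and hypoglycemia, but not genital infections.

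On subgroups, SAP section 4 limits the safety breakdowns to "AEs and AEs of special interest, in the subgroups LVEF" below versus at or above 45%, and SAP Table 2-1 lists LVEF only. Sex by arm is tabulated among the baseline characteristics, in the FAS (SAP 2.3.2).

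**The concern.** A vulvovaginal infection can occur only in women. A percentage with men in the denominator describes the whole arm, but it does not tell a reader how often the event occurs in patients who can have it. For most preferred terms this does not arise. Here it touches a harm the sponsor already attributes to experience with the drug, so a usable rate by dose is worth having.

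Three consequences need checking: how far the tabulated rate and risk difference fall below those in women, whether the 10% display can leave the event out, and whether a chance difference in the share of women between arms distorts the dose comparison.

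**Working it through.** **Inputs.** Planned arms follow from 496 patients at 1:1:2:2:2 (Protocol 9.8, SAP section 3): 496/8 = 62, giving 62, 62, 124, 124 and 124, as stated. The documents give neither the share of women, f, nor the infection rate in women, p. Both are assumed below, f mainly at 30% to 50%. Arm sizes after early termination are not given either.

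**Rate.** For an event possible only in women, the all-patient percentage is f × p. With p = 10%:

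| f | Tabulated on all patients | Tabulated on women |
|---|---|---|
| 30% | 0.30 × 10% = 3.0% | 10% |
| 40% | 0.40 × 10% = 4.0% | 10% |
| 50% | 0.50 × 10% = 5.0% | 10% |

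**Risk difference.** With the same f in both arms, the difference is f × (p1 − p2). For 10% against 3% in women at f = 30%, 7 points become 0.30 × 7 = 2.1 points. The risk ratio is unchanged, because f cancels.

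**The 10% display.** A term enters if it reaches 10% of patients in any arm. The rate in women needed is 0.10/f: 33% at f = 30%, 25% at f = 40%, 20% at f = 50%.

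**Arm comparison.** If f differs between arms, the crude ratio is the true ratio multiplied by f1/f2. With no drug effect, binomial simulation of 62 against 124 patients gives a 95% range for f1/f2 of 0.60 to 1.57 at f = 30% and 0.72 to 1.34 at f = 50%. That range must be set beside the noise from small event counts. Simulating events as well, at f = 30%, with equal rates in women and keeping draws with at least one event in each arm:

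| Rate in women | 95% range of ratio, all patients | 95% range of ratio, women only |
|---|---|---|
| 10% | 0.29 to 6.00 | 0.30 to about 5.4 |
| 20% | 0.22 to 3.33 | 0.25 to about 3.2 |

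At a 10% rate the expected counts are 62 × 0.30 × 0.10 = 1.9 and 124 × 0.30 × 0.10 = 3.7. The women-only denominator narrows the range a little; neither denominator supports a firm comparison of doses.

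**The case against.** Several points on the other side stand.

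- SAP 2.6.2.2 says only that these events are summarised; it names no denominator. The all-patient percentage is inferred from Protocol 9.5.2, the SAF definition, SAP 2.6.2.1 and the absence of any sex-specific denominator. Table shells and the case retrieval sheet are outside the documents. The inference is firm for the general preferred-term tables and less so for the special-interest table.
- The risk category is genital infections, which men can have too. The whole-arm denominator is right for that row.
- The 10% cut governs one display. The full preferred-term table and the special-interest table have no threshold, and events are also listed by patient. A reader might infer that the plan can lose this harm from the report; it cannot.
- A reader might also infer that the arm comparison is biased. Randomisation gives every arm the same expected share of women, so any shift is chance, and event-count noise is much larger. The SAP specifies no test for genital infections.
- The rate in women can be approximated by dividing term counts by the number of women per arm. The sex table uses the FAS by randomised arm while AEs use the SAF by treatment received, so the match is close but not guaranteed.
- The study stopped early and the SAP cut its subgroups for that reason. Smaller arms mean few women per arm.

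These points narrow the concern. They do not remove the dilution of the rate and risk difference for female-only terms, and they give no reason to leave readers to reconstruct the rate across two analysis sets.

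**Conclusion.** The point holds as a cheap reporting improvement. Following the SAP as written, female-only genital infection terms are shown as a percentage of all dosed patients in the arm, and male-only terms are affected in the same way. For vulvovaginal infection the tabulated rate and risk difference are 0.3 to 0.5 times those in women if women make up 30% to 50% of an arm. The term misses the common-event table unless some arm has 33% to 20% of its women affected. These sizes rest on the assumed share of women and on the plain reading of the denominator.

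The gain from the change is mainly a correct absolute rate and risk difference; for arm comparisons it is modest. No planned test is affected and no passages conflict. This concerns how a table is built, not how patients are managed.

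**What to change.** In SAP 2.6.2.2, keep the pooled genital infections row on the whole SAF arm and add a sentence requiring genital infections by sex, with women in the SAF arm as denominator for women and men in the SAF arm for men. In SAP 2.6.2.1, state that the 10% cut for preferred terms specific to one sex is applied to that sex's denominator. In SAP section 4, note this as an exception to the LVEF-only breakdown.

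Sex is already collected, so no new data are needed. The cost is one or two sentences and one extra table. Its cells will be small, more so after early termination, so counts should be shown beside percentages and differences between doses read with caution.

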### 3.3 Rationale for dose/regimen, route of administration and duration of treatment

LIK066 has been studied in multiple clinical trials with a variety of dosing regimens using either single or multiple daily doses at durations of up to 12 week in healthy subjects, patients with T2DM and obese patients.

Since the objective is to find a dose with sub-optimal to optimal effect on SGLT1 and SGLT2 inhibition in the kidney, but with no or minimal gut effect to minimize the risk of diarrhea, LIK066 50mg qd is selected as the highest dose for this study.

To minimize the risk of GI adverse effects of the SGLT1 inhibition in the gut such as diarrhea, the LIK066 dose will not be taken around mealtime; hence dose administration is recommended at bedtime. The 10mg dose is selected between the low and top dose in the study and to enable exploration of the shape of the dose-response curve.

Based on results from previous exploratory phase II studies in HF comparing sacubitril/valsartan with valsartan (e.g. LCZ696B2214; [Solomon et al, 2012](#)), treatment with LIK066 for a duration of 12 weeks would be expected to be sufficient in order to reveal a significant change in NT-proBNP. Twelve weeks after introducing an anti-diabetic treatment is an accepted time point for initial evaluation of drugs' effect on glycemic control (HbA1c). The full duration of exposure of 36 weeks will provide data for parameters requiring longer follow-up to be evaluated (echocardiography) as well as safety data.

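### The diarrhoea day count adds up AE records, not distinct calendar days, and is summarised only for affected patients, so it can overstate days and does not by itself show burden per treated patient

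*SAP*

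**What the plan says.** SAP 2.6.2.2 singles out diarrhoea, with ketoacidosis and hypoglycaemia, for additional analyses. The length of one episode is set by "Number of days for one diarrhea incidence = AE end date – AE start date +1", so both the first and the last day count. The patient's total is the "sum of days on diarrhea over all incidences that occurred in the double-blind period". The total is restricted to affected patients: "Number of days with diarrhea events will be calculated for all patients with at least one diarrhea incidence". It is summarised descriptively by treatment.

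SAP 2.6.2.1 adds a recording rule: "An AE with increased severity should be considered and recorded as a new AE". Neither document gives a rule for closing the milder record when severity rises, for merging records that overlap or adjoin, or for counting a calendar day once.

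The same part of SAP 2.6.2.2 also gives the number and percentage of patients with diarrhoea by treatment in seven time windows. Diarrhoea is one of the risk categories in the table of AEs of special interest by treatment.

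**The concern.** The output is presented as a number of days with diarrhoea, but the formula counts record-days. The two agree only when no two of a patient's records share a day. A worsening creates a second record by design, so shared days are a foreseeable result of the plan's own rule. Protocol 7.1 also requires each AE to be followed until it resolves or is judged permanent. A site could reasonably read that as leaving the milder record open through the worse phase.

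The second issue is the denominator. Patients with at least one episode are a group formed after randomisation. A mean over that group describes how long diarrhoea lasts in those who get it. It does not describe how much diarrhoea an arm experiences.

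The measure is worth getting right because diarrhoea bears on the choice of dose. Protocol 3.3 selects the highest dose to act on the kidney "with no or minimal gut effect to minimize the risk of diarrhea", and explains bedtime dosing on the same ground. A reader comparing arms on this table should know what is being counted.

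**Working it through.** The documents give no diarrhoea incidence, duration or rate of worsening, so there is no stated figure to reproduce. The episodes and event counts below are assumptions. The formulas come from SAP 2.6.2.2, and the arm size of 124 (placebo and LIK066 50 mg) is the planned size in SAP 3.

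**Step 1: record-days against calendar days.** Take one episode lasting from day 1 to day 10, so 10 distinct calendar days. The SAP total is the sum of (end − start + 1) over records.

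| How the milder record is closed | One worsening (day 4) | SAP total | Two worsenings (days 4 and 7) | SAP total |
|---|---|---|---|---|
| Day before the worsening | 1–3, 4–10 | 3 + 7 = 10 | 1–3, 4–6, 7–10 | 3 + 3 + 4 = 10 |
| Same day as the worsening | 1–4, 4–10 | 4 + 7 = 11 | 1–4, 4–7, 7–10 | 4 + 4 + 4 = 12 |
| Left open to resolution | 1–10, 4–10 | 10 + 7 = 17 | 1–10, 4–10, 7–10 | 10 + 7 + 4 = 21 |

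The excess over 10 days is zero, one day per worsening, or the whole overlap (7 days, or 70%, with one worsening; 11 days with two). The patient's experience is the same in every row. A count of distinct days gives 10 throughout.

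**Step 2: affected-only mean against the mean over all treated patients.** These are linked by

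mean over all treated = incidence × mean over affected.

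Suppose arm A has the shorter mean among affected patients, m_A < m_B. Arm A still has more days per treated patient when p_A × m_A > p_B × m_B, that is, when p_A / p_B > m_B / m_A. With assumed means of 5 days on 50 mg and 8 days on placebo, the threshold is 8/5 = 1.6.

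| Affected, 50 mg | Affected, placebo | Incidence ratio | Days per treated patient, 50 mg v placebo | Order differs from 5 v 8? |
|---|---|---|---|---|
| 25/124 | 5/124 | 5.0 | 125/124 = 1.01 v 40/124 = 0.32 | Yes |
| 25/124 | 12/124 | 2.1 | 1.01 v 96/124 = 0.77 | Yes |
| 25/124 | 20/124 | 1.25 | 1.01 v 160/124 = 1.29 | No |

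**Step 3: an error in the other direction.** SAP 5.1.2 imputes no end date for an ongoing AE, so the duration formula returns no value for it, and SAP 2.6.2.2 does not say how such an episode enters the total. Take four affected patients with assumed episodes of 5, 5, 5 and 60 days to date, the last still ongoing. The mean is 75/4 = 18.75 days, but only the three closed episodes can be used, giving 5. The net direction of error therefore cannot be read from the overlap problem alone.

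**The case against.** Several points on the other side are sound.

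- A reader might infer that the SAP does double count. It does not say so. If sites close the milder record the day before the worsening, the excess is zero. The closing convention may be set in eCRF instructions that are not among these documents.
- The worsening rule is introduced by "The following rules apply to the above AE summaries", ahead of the diarrhoea section, so its reach could be disputed. The objection is weak: the rule says how an AE is recorded, and the diarrhoea count is built from those records.
- A reader might infer that preferred terms within the diarrhoea category also overlap. That depends on the retrieval sheet to which SAP 2.6.2.2 refers, and the sheet is not available here.
- A reader might infer that the table hides or reverses a dose-related burden. The SAP never calls the affected-only figure burden. Its standard descriptive set (SAP 2.1) includes n, and incidence by arm appears in the special-interest table. Multiplying that incidence by the affected-only mean largely recovers days per treated patient.
- No passage makes this count the main tolerability measure. It is one untested table beside those for incidence, severity, interruption and discontinuation, in an abbreviated report after early termination.

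Two things survive. Multiplication recovers a mean only: it gives no median or quartiles over all treated patients, does not remove any overlap, and takes no account of exposure, which early termination may have made uneven. The SAP specifies exposure-adjusted rates for hypoglycaemia but not for diarrhoea days. And the formula as written is not a count of days whenever two records share a day.

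**Conclusion.** The point holds as a defect of definition and labelling. The formula overcounts whenever a patient's diarrhoea records share a calendar day, by nothing, one day per worsening, or the full overlap, depending on a closing convention that neither document states. Double counting is possible, not established.

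The affected-only summary is a legitimate description of duration. It becomes misleading only if read alone as burden, and the two orderings differ only when the incidence ratio exceeds the inverse ratio of the mean durations (1.6 in the example).

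That overcounting grows with dose should not be inferred: the documents contain no figure on how often diarrhoea worsens in any arm, and ongoing episodes pull the other way. All episode lengths and event counts above are illustrative. The consequence is limited to one descriptive safety table, and no hypothesis test or decision rule in the SAP uses it. The change is worth making mainly because it is so cheap.

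**What to change.** In SAP 2.6.2.2:

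1. Define a patient's diarrhoea days as the number of distinct calendar days in the double-blind period covered by at least one diarrhoea record (the union of the intervals).
2. State the cut-off date applied to episodes without an end date, so that they enter the count.
3. Keep the present summary and label it as duration among affected patients.
4. Add a descriptive line by treatment over all safety-set patients, with zero for those without diarrhoea, or give days per 100 patient-days of exposure in view of the early termination.

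The cost is a few sentences of SAP text and a few lines of programming. AE dates and exposure are already collected, and no other analysis changes.
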